8.0 DATA ANALYSIS

The data coordinating center will provide access to data and resources to facilitate analysis of OAI data by the scientific community.

8.1 Public Website for Access to OAI Data and Images

Potential users will obtain access to data and images through a public website (http://www.oai.ucsf.edu/datarelease/) developed and maintained by the data coordinating center. This site will provide general information about the OAI and its design, describe the study data, procedures and materials, provide online access to forms, operations manuals and data documentation, and enable limited online data exploration. Clinical data sets will be made available for download to registered users through the web site. Joint images will be distributed on various electronic media. Access to biological specimens will be by application to the NIAMS-administered Biospecimen Resource Allocation Committee (See Section 9.7.) The planned major features of the website are listed below.

Study information.

- Description of OAI information about the study, investigators and participating organizations;
- Links links to participating organizations and arthritis-related web sites and required plug-ins for interacting with the web site;
- Q&A a form for submitting a question about the study, and a searchable archive of previously asked questions and their posted answers;
- Help instructions for using the Web site and experiencing full functionality.

Data description.

- description of available public use OAI data sets;
- data documentation (downloadable) variable distributions, data documentation and metadata, forms, operations manuals;
- data documentation (online) search on keywords or browse through categories of related variable content;
- custom datasets (downloadable) small datasets based on subsetting criteria set by the user will be programatically created and made available to download from the website.
- data exploration an online query and reporting tool (SAS) for generating simple reports and tables of OAI data in real-time.
- requests for images a section of the website will detail the procedures for requesting joint images.

Study data and materials access.

- user registration and user agreements;
- guidelines for data and image distribution;
- automated submission of data and image requests;
- analysis user's guide documentation on known data-related issues pertinent to statistical analysis;
- biospecimen access guidelines and link to Biospecimen Resource Allocation Review Committee;
- clearing house for publications and analysis plans using OAI data;
- bulletin board a forum for facilitating discussion and collaboration in the use of OAI data and materials.

The coordinating center will also host OAI data users meetings during the study.

Public data releases will generally occur within 6 to 12 months after the end of clinic visits for each of the first half of cohort and for the entire cohort. Hence there will be at least two data releases for each visit cycle.

8.2 Analytical and Statistical Issues

8.2.1 Key Research Questions Driving the Study Design

The design of the OAI and the data being collected will allow users to develop and evaluate OA biomarkers and to describe the natural history of OA and investigate factors that shape it. It is not practical to anticipate all of the potential uses of the data, nor all the types of analysis that will be performed to address user defined questions. However, the following are examples of the types of research questions that data users will be able to address:

- In knees with symptomatic OA at baseline, determine the relationship of:
 - baseline imaging structural markers, biochemical markers and risk factors with progression of symptoms and disability;
 - baseline imaging structural markers, biochemical markers and risk factors with progression of joint space loss assessed by x-ray and with loss of cartilage assessed by MRI;
 - changes in imaging structural markers and biochemical markers during the study with progression of symptoms and disability;
 - changes in imaging structural markers and biochemical markers during the study with progression of joint space loss assessed by x-ray and with loss of cartilage assessed by MRI.
- In knees without symptomatic OA (including those with subclinical disease) at baseline, determine the relationship of:

- baseline imaging structural markers, biochemical markers and risk factors with the onset of knee OA, defined in various ways (e.g. symptomatic OA, specific structural abnormalities, symptom onset, etc.);
- changes in imaging structural markers and biochemical markers during the study with the onset of knee OA defined in various ways (e.g. symptomatic OA, specific structural abnormalities, symptom onset, etc.);
- baseline imaging structural markers, biochemical markers and risk factors with progression of joint space loss assessed by x-ray and with loss of cartilage assessed by MRI.

8.2.2 Assessment of Images Needed for Key Research Questions

The OAI will obtain selected readings and measurements from the joint images acquired during the study and make these available to investigators. However, given the very large number of images that will be acquired over the course of the study (Tables 4,1 and 5.1, e.g. over 40,000 separate knee MRI exams and over 40,000 separate knee radiograph exams) only a fraction of the images will be included in these assessments, and the measurements will only be a subset of all the types of measurements desired by investigators. Instead, the OAI will make available in the public use data sets a limited number of image assessments in subjects selected to enable investigators to address the broad types of questions posed above. In addition, all joint images will be available for user-defined assessments and measurements.

8.2.2.1 Clinic reader assessment of baseline knee radiographs in the entire cohort

In order to assign participants to the appropriate subcohort and to exclude individuals with bilateral severe joint space narrowing, the following evaluations will be performed for each knee by readers at the clinical sites using the baseline fixed flexion knee radiograph:

- the presence of definite tibiofemoral osteophytes (OARSI atlas grade 1-3,); and
- mild to moderate (OARSI grade 1-2) or severe (OARSI atlas grade 3 or 'bone on bone') joint space narrowing in the medial and lateral tibiofemoral compartments of each knee.

8.2.2.2 Central assessment of joint images in the Progression subcohort

Progressive disease in those with symptomatic knee OA at baseline will be common,(73, 129) and the OAI will undertake longitudinal evaluation of knee images in those with baseline prevalent symptomatic disease, the group most likely to be a target of treatment interventions. Potential assessments for Progression subcohort knees include:

- Knee radiographs: quantitative measurement of the medial and lateral tibiofemoral joint space and qualitative assessment of structural features of OA at baseline and follow-up;
- Knee MRIs: quantitative measurement of cartilage volume and thickness at baseline and follow-up; qualitative assessment of structural features of OA at baseline;
- Hand radiographs: presence and severity of baseline hand OA;
- Pelvis radiographs: presence and severity of baseline hip OA.

8.2.2.3 Central assessment of joint images in the Incidence subcohort, nested case-cohort design

Since the rate of onset of knee OA, even in those at high risk, will be relatively low, efficiencies can be gained and little information lost by targeting those subjects who develop new disease and comparing them to selected subjects at risk who don't (instead of intensively studying all of those without disease). As with other measurements that can be prohibitively expensive in large cohorts, such as biochemical marker assays, a nested case-cohort or case-control approach to assessing joint images is an efficient alternative to the evaluation of predictor-outcome relationships in longitudinal data sets.(130) Studies suggest that one approximates the statistical power of evaluating the entire cohort by studying cases and a large number of controls (usually 4) per case. This approach requires articulating specific research questions, as in Section 8.2.1, in order to define the predictors and endpoints and to estimate the sample size needed for measurements.

To identify cases of incident radiographic and symptomatic knee OA, a central reading of the followup fixed flexion knee radiographs will be performed in order to identify new tibiofemoral osteophytes, a component of the study definitions of incident radiographic and incident symptomatic knee OA (the first occurrence during the study of frequent knee symptoms and definite tibiofemoral osteophytes in the same knee).

A commitment to specific definitions of incident disease is also a potential disadvantage of the casecohort design. While alternative definitions of endpoints can be studied within a planned sample of cases, power will be limited for smaller subsets of endpoints and there is a potential for bias in the subsamples of cases. However, since alternative endpoint definitions are likely to be highly correlated with a primary endpoint (e.g. symptomatic OA), the definition of incident endpoints can be expanded to yield additional and different cases with modest increases in numbers and cost.

Potential central assessments for incident OA knees and control knees include:

- Knee radiographs: quantitative measurement of the medial and lateral- tibiofemoral joint space at baseline and follow-up.
- Knee MRIs: quantitative measurement of cartilage volume and thickness at baseline and follow-up; qualitative assessment of structural features of OA at baseline;

- Hand radiographs: presence and severity of baseline hand OA.
- Pelvis radiographs: presence and severity of hip OA.

Figure 8.1. Potential central assessment of images

8.2.2.4 Methods for central image assessments

Specific assessments, measurement methods and protocols will be recommended by the Steering Committee.

The data coordinating center will contract with vendors to make measurements on joint images. All centrally funded and acquired measurements will be made available as part of the OAI public release databases.

Importantly, all of the study images will be archived and available for investigations of user-defined endpoints and to extract alternative and novel structural markers.

8.2.3 Biomarker and Surrogate Validation: Statistical Issues

The usually accepted definition of a surrogate marker is a measure which can substitute for a more difficult, distant, or expensive-to-measure endpoint in predicting the effect of a treatment or therapy in a clinical trial.(131) Greatly complicating the issue is the fact that all the definitions of surrogacy revolve around the elucidation of the joint and conditional distributions of the desired endpoint, putative surrogate and their dependence on a specified therapy.(131-135) Therefore, what may work adequately for a given endpoint and one type of therapy may not be adequate for the same endpoint and a different type of therapy.(135) The OAI is an observational study, not a clinical trial, and it will be impossible to anticipate all the potential therapies for which a surrogate marker might be desired.

Nevertheless, as measurements are developed that capture more and more accurately the structure, functioning and tissue metabolism of the joints, it will become more likely that proposed biomarkers are on the causal pathway to OA and its clinical outcomes and can function as surrogate markers for at least one element of disease. Furthermore, the longitudinal nature of the OAI allows correlation of changes within a person over time between different elements of disease including different measures of structural change, such as radiographic and MRI findings, and disability and pain. So that the OAI will support analyses that researchers may want to perform to evaluate putative biomarkers and assess their potential for surrogacy, it is designed to have adequate precision for estimating the joint relationship between proposed biomarkers and desired endpoints. At the very least, investigators will be able to identify a number of promising biomarkers for use in early development of treatments and that can be tested – or 'validated' – in trials as surrogates for treatment effects. These initial objectives for surrogacy may require somewhat different validation standards in comparison to use of surrogates by regulatory authorities in registering a new drug treatment.

Surrogacy means more than a demonstrable or even a strong association between the desired endpoint and the proposed surrogate(135) and original definitions have been criticized as being limited in scope and having fundamental shortcomings.(132, 133, 135) Recent proposals in the context of meta-analysis get more to the heart of surrogacy.(134) By correlating changes in the surrogate with changes in a primary endpoint, these approaches more directly address the surrogacy question. These analytic techniques are equally applicable in a longitudinal setting, such as the OAI.

The techniques for doing so are most easily described in the context of a continuous surrogate (e.g. change in cartilage volume) and a continuous outcome (e.g. changes in WOMAC score or joint space width). Linear mixed models (136)with random slopes (or, more generally, random functions) and intercepts through time are built for both the surrogate marker and the endpoint. That is, the joint distribution of the surrogate marker and the endpoint are modeled using the same techniques as used for each variable individually. The degree to which the random slopes for the surrogate and the endpoint are correlated give a direct measure of how well changes in the surrogate correlate with changes in the endpoint.(134) The ability of the surrogate to extinguish the influence of potent risk factors, such as obesity or being female, in a multivariate model, further strengthens its use as a surrogate marker.

A typical analysis of candidate surrogate biomarkers using OAI data will fully utilize repeated measurements of an outcome variable, such as WOMAC score, and/or correlated measurements

assessed in two knees, while accounting for the correlation of measurements within an individual. In a typical knee-based analysis, clustered data techniques will be used (i.e., mixed effects models, frailty models - the primary methods for clustered survival analysis - or GEE methods(136)) to adjust for the within person correlation between the two knees.

Continuous outcome measurements, such as WOMAC disability score or joint space width, might be analyzed with mixed linear models with terms for time, interactions with time, predictors such as change in cartilage volume, and confounders such as gender. The time effect captures the rate of decline and a time interaction with a biomarker or risk factor describes how these predictors modify the rate of decline in the continuous outcome.

Similarly, dichotomous outcomes might be modeled using a logistic function with random slopes and intercepts and fit using a nonlinear mixed model program such as SAS Proc NLMIXED (SAS, Version 8). Time-to-event variables, such as incident symptomatic OA, could be analyzed using the discrete-time Cox proportional hazards model with time-varying covariates (a GEE version of this model would be used for knee-based analyses). Predictors of interest might include terms like cartilage volume and possible confounders, or effect modifiers, such as gender. The assumption of proportional hazards can be assessed by including interactions with time and functions of time.

In practice, it is likely there will often be competing candidate surrogate markers each correlated to a different degree with the endpoint. The preferred surrogate is one that is biologically defensible and most highly correlated with the endpoint. The statistical significance of the differences between correlations can be evaluated using a parametric bootstrap.(137)

8.2.4 Expected Rates of Knee OA Incidence and Power for Analyses of Incident Disease

Table 8.1 shows the number of subjects and knees that are expected to develop incident symptomatic knee OA during four years of follow-up in the Incidence subcohort. For the purpose of these estimates, incident symptomatic knee OA is defined as the first occurrence in a knee of frequent knee symptoms (pain, aching or stiffness on most days of at least one month during the past 12 months) and definite tibiofemoral osteophytes in the same knee. Expected incidence is estimated by applying age and gender-specific incidence rates, derived from analyses modeling enrichment of the cohort using risk factors (See Appendix B for details), to the original goals for enrolled subjects in each gender and age stratum (Appendix A). The base age- and gender-specific incidence rates used in the cohort enrichment modeling are taken from published estimates from the Fallon Community Health Plan(35) and the Framingham study.(20, 22) Cumulative loss to follow-up is assumed to be 28% by the end of year 4; 10% dropout at the first follow-up visit and 7% additional dropout in each year after that. Similar calculations are used to estimate the expected number of incident knees, taking into account the ratio of bilateral to unilateral incidence from the Framingham study (unpublished).

The overall incidence of symptomatic knee OA expected among subjects selected for the OAI Incidence subcohort is 1.8/100 person-years in men and women combined. Adjusted age-specific risks range from about 1.0/100 p-y at age 45-49 to about 2.0/100 p-y in those age 60 and over and are similar by gender. This compares with an observed range in age-specific risks of about 0.2/100 p-y to

0.8/100 p-y in the general population in the same age strata.(35) Cumulative incidence after 4 years is expected to be about 5.5%.

It is likely that these are conservative estimates. The increased risk in the overweight groups derived from the cohort enrichment modeling suggest a smaller effect of weight than is seen in the existing incidence studies. In the Fallon Health Plan, women (mean age 60) who weighed 175 lbs or more had a 5 to 6 fold increased risk of incident clinical knee OA compared to those who weighed less.(138) In the Bristol cohort, men and women in the highest third of BMI (≥ 25.4 kg/m2) had at least a 9-fold higher risk of developing knee OA than those in the lower third.(15) This compares to a risk ratio of 2.0 for prevalent symptomatic knee OA in the upper third of weight in Framingham women and 1.6 for the upper third of weight in men (Appendix B).

Most participants in this subcohort will have two knees at risk for incident disease, and consistent with this the number of knees with incident symptomatic OA (Table 8.1) is projected to be greater than the number of incident case subjects.(20) (and unpublished data) In addition, contralateral knees in the Progression subcohort that are free of prevalent disease at baseline have a high risk of developing OA(139) and may be pooled with cases from the Incidence subcohort for some analyses.

	Subjects with	Knees with
Gender/	Incident Sx OA	Incident Sx OA
Age stratum	Ν	N (%)
Men age 45-69	73	121 (32%)
Men age 70-79	37	62 (17%)
Men age 45-79	110	183 (49%)
Women age 45-69	76	127 (34%)
Women age 70-79	37	61 (17%)
Women age 45-79	113	188 (51%)
All subjects	223	371 (100%)

Table 8.1 Expected number of cases of incident symptomatic knee OA based on enrollment goals in the Incidence subcohort

Incident radiographic OA (the first occurrence of tibiofemoral osteophytes in knees free of this finding at baseline) is another potential endpoint of interest in this subcohort. The age- and gender-specific incidence of radiographic knee OA, without taking knee symptoms into account, is expected to be about 2.3 to 2.6 times greater than the incidence of symptomatic knee OA.(20) Assuming that one-third of subjects in the Incidence subcohort will already have radiographic knee OA at baseline in at least one knee, over 550 knees are expected develop incident radiographic OA during follow-up.

Occurrence of incident symptomatic OA for knees in the same subject is correlated, so the equivalent number of independent incident knees is smaller. To reflect this, the projected number of incident knees is divided by 1 plus the interclass correlation coefficient to obtain the equivalent number of independent knees.(140) Using the 0.4 interclass correlation for prevalent symptomatic knee OA in the Framingham cohorts, the equivalent of 265 independent knees with incident symptomatic OA is expected by the end of the fourth year of follow-up.

Table 8.2. Power for dickof incident Sx OA obta	L
Exposure	Relative Risk
Prevalence	detectable with
(%)	80% power
50	1.43
33	1.45
25	1.49
10	1.70

Based on expected numbers of endpoints using the original study design assumptions, the power to detect relative risks (RR) between exposed and nonexposed subjects in the Incidence subcohort is displayed in table 8.2. The smallest detectable RR by Cox regression of time to incident OA using a two-sided 0.05 hypothesis test with 80% power is given for dichotomous exposures of 10%, 25%, 33% and 50% prevalence in the table. (In reality, incident cases will accrue on an annual basis and would be analyzed

using a grouped failure time model.)

Figure 8.2 shows the power curves by smallest detectable RR value for each of these exposure prevalence values. Detectable relative risks will be smaller for more common endpoints, such as incident radiographic OA.

Figure 8.2

OAI Power for Incidence of Symptomatic Knee OA

Analyses of structural biomarkers for incident OA will use only the knees from the nested case-control sample, which will have full marker information. (A similar approach will likely be applied to analysis of biochemical markers and incident OA.) Table 8.3 shows relative risks that could be detected in a

Table 8.3 Power for dic of incident Sx OA in c	-
Exposure	Relative Risk
Prevalence	detectable with
(%)	80% power
50	1.56
33	1.57
25	1.62
10	1.91

nested case-control analysis using an MRIderived risk factor or a biochemical marker as a predictor of time to incident OA. For this it is conservatively assumed that image or biochemical marker data would be available from about 300 case knees and 1200 control knees. Because the number of cases and controls is reduced in the case-control analysis, the detectable relative risks are larger. Even for exposures with 10% prevalence, there is 80% power to detect a relative risk of 1.62 in all subjects, and 1.91 in the case-control analyses.

Analysis of the association of biomarkers with incident OA to evaluate surrogacy, in the case-cohort sample with full biomarker data, might consider the correlation between the time trend in the biomarker with time trend in log odds of incident OA from a logistic regression model having a random slope (fit using the SAS NLMIXED procedure). These trends are estimated with some error, due to instrument-specific measurement error, making the observed correlation values have some bias toward 0. The accuracy calculations below take this attenuation toward 0 into account.

To select the most promising biomarkers, 95% confidence intervals could be used, and Table 8.4 displays results for the attenuated correlation values. Confidence intervals for the correlations are found using Fisher's Z-

transformation.(141) The table uses the MRI cartilage volume, which has an interclass correlation of 0.92 at the medial tibia,(142) as an example biomarker. Table 8.4 shows various correlation values between time trends in the first column, the attenuated correlation (allowing for measurement error) in the second column,

time trend for	Table 8.4 Precision of attenuated correlations betweenime trend for cartilage volume change and the time trendin log odds of incident symptomatic OA				
True	Attenuated	95% CI for Attenuated			
Correlation	Correlation	Correlation			
0.20	0.196	(0.136, 0.254)			
0.40	0.393	(0.340, 0.444)			
0.60	0.589	(0.548, 0.628)			
0.80	0.786	(0.761, 0.808)			
0.90	0.884	(0.870, 0.897)			

and the 95% confidence interval (CI) for the attenuated correlation in the third column. These results show that correlations with incident OA will be estimated with good precision, having confidence interval widths close to 0.1 for moderate correlation values.

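### Section 8.2.4 gives two detectable relative risks for one case: 1.70 in Table 8.2 and 1.62 in the sentence after Table 8.3

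*Protocol*

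**What the plan says.** Section 8.2.4 of the protocol introduces Table 8.2 as showing "the power to detect relative risks (RR) between exposed and nonexposed subjects" in the Incidence subcohort, using the expected numbers of endpoints under the original design assumptions. The quantity tabulated is the "smallest detectable RR by Cox regression of time to incident OA using a two-sided 0.05 hypothesis test with 80% power", and it "is given for dichotomous exposures of 10%, 25%, 33% and 50% prevalence in the table". The four entries are 1.43 (50%), 1.45 (33%), 1.49 (25%) and 1.70 (10%).

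Table 8.3 gives the corresponding values for the nested case-control sample, assumed to have about 300 case knees and 1,200 control knees: 1.56, 1.57, 1.62 and 1.91 in the same order.

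The text beside Table 8.3 explains that detectable relative risks are larger in the case-control analysis because it uses fewer knees. It then compares the two designs at 10% prevalence: "Even for exposures with 10% prevalence, there is 80% power to detect a relative risk of 1.62 in all subjects". For the nested design, the figure given in that sentence is 1.91.

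**The concern.** The closing sentence restates the 10% rows of the two tables. Its case-control figure agrees with Table 8.3. Its whole-cohort figure does not agree with Table 8.2, although population, endpoint, prevalence and power are the same. One of the two values must be wrong.

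The protocol is written largely for outside analysts of a public resource, and this sentence is the plain-language statement of what the Incidence subcohort can detect for a less common exposure. An analyst who plans from 1.62 when 1.70 is right will expect more power than the study offers. The difference also carries through Table 8.5, which tells users to raise the detectable ratio to a stated power when cases fall short. For 20% fewer cases (power 1.11), 1.62 becomes 1.62^1.11 = 1.71, while 1.70 becomes 1.70^1.11 = 1.80.

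**Working it through.** **Inputs, all from section 8.2.4.** Tables 8.2 and 8.3 as listed above; two-sided 0.05 and 80% power; 223 case subjects and 371 incident knees (Table 8.1); correlation 0.4 between knees; 28% cumulative loss to follow-up. The goal of 4,000 in the Incidence subcohort is from section 4.5.

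**Step 1: the protocol's own event count.** 371 / (1 + 0.4) = 265. This reproduces the statement that "the equivalent of 265 independent knees with incident symptomatic OA is expected by the end of the fourth year of follow-up".

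**Step 2: compare the two tables row by row.** If one method underlies both tables, the ratio of log relative risks, Table 8.3 over Table 8.2, should be roughly constant.

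| Prevalence | Table 8.3 | Table 8.2 | ln / ln | Ratio |
|---|---|---|---|---|
| 50% | 1.56 | 1.43 | 0.445 / 0.358 | 1.24 |
| 33% | 1.57 | 1.45 | 0.451 / 0.372 | 1.21 |
| 25% | 1.62 | 1.49 | 0.482 / 0.399 | 1.21 |
| 10%, using 1.70 | 1.91 | 1.70 | 0.647 / 0.531 | 1.22 |
| 10%, using 1.62 | 1.91 | 1.62 | 0.647 / 0.482 | 1.34 |

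The value 1.70 fits the pattern and 1.62 does not.

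**Step 3: can both figures have 80% power?** The protocol names Cox regression but no power formula, so several were tried at 10% prevalence.

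| Calculation | Power at 1.62 | Power at 1.70 |
|---|---|---|
| Schoenfeld, 265 events | 65.4% | 73.6% |
| Schoenfeld, 371 unadjusted knees | 79.6% | 86.6% |
| Schoenfeld with exposure share among events, 265 | 80.6% | 88.4% |
| Two proportions, 265 events, N = 4,000 | 79.7% | 86.7% |
| Two proportions, 223 events, N = 4,000 | 73.0% | 80.8% |
| Two proportions, 223 events, N = 2,880 (4,000 × 0.72) | 74.0% | 81.7% |

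No calculation gives 80% for both. Plain Schoenfeld on 265 events gives a detectable value of exp(2.802 / √(265 × 0.10 × 0.90)) = exp(0.574) = 1.775, which is neither figure.

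**Step 4: which figure belongs with the rest of Table 8.2?** With 223 events among 2,880, the four rows of Table 8.2 have 78.6%, 80.4%, 81.5% and 81.7% power, all within 2 points of 80%. At 10% prevalence in that calculation, 1.62 has 74.0%. A case-control two-proportion calculation on 300 and 1,200 fits the four rows about equally well (78.6%, 79.9%, 80.7%, 79.8%) and gives 1.62 about 71.7%. The fit therefore does not identify the method used, but under both calculations 1.70 sits with its neighbours and 1.62 does not.

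**Step 5: size of the gap.** With the variance term held fixed, required events scale as 1 / (ln RR)². The ratio is (0.531 / 0.482)² = 1.21. Schoenfeld at 10% prevalence agrees: 7.849 / (0.09 × 0.482²) gives 375 events for 1.62 and 7.849 / (0.09 × 0.531²) gives 310 for 1.70 (unrounded logarithms used), and 375 / 310 = 1.21.

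**The case against.** The best defence is that this is a slip in one sentence, with the conflicting value printed in the same section. The text introduces the table as the place where power is shown, and the tables' own pattern supports the table. The study is observational, its analyses are user-defined, and enrolment was nearly complete when this version was written. All of that stands, and it is why the impact is minor. It does not remove the contradiction, since no reading of the sentence makes 1.62 agree with Table 8.2. Taking the phrase about all subjects to include contralateral knees from the Progression subcohort does not help: the protocol says only that such knees may be pooled for some analyses, and gives no event count for the pool.

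A reader might be tempted to infer more, but the documents do not support it:

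- **That the effective event number of 265 is wrong.** The mismatch shows nothing of the kind; 371 / 1.4 = 265, as stated.
- **That Table 8.2 is itself wrong because plain Schoenfeld gives 1.775.** The formula is not named, and the answer at 10% prevalence depends on it: on 265 events a score-test version gives 1.65 and a Wald version about 1.62. This spread shows dependence on method and does not convict the table. Equally, the Wald result means 1.62 cannot be ruled out from outside.
- **That the figures must be cut for lower enrolment.** Table 8.2 is expressly tied to the original assumptions, and section 8.2.4.1 with Table 8.5 deals with shortfalls separately.

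**Conclusion.** The point holds as an internal contradiction: for one population, endpoint, prevalence, power and significance level, section 8.2.4 states both 1.70 and 1.62. The statement is wrong as written, and this can be seen by setting the sentence beside Table 8.2.

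That 1.70 is the value consistent with the tables, and that the sentence therefore overstates sensitivity for rare exposures, is probable but inferred. It rests on the assumption that one method underlies all rows of each table. A misreading of the 25% row of Table 8.3 would explain the 1.62, but so would a leftover from another calculation.

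The size is 0.08 in relative risk, or about 21% in events under inverse-square scaling of the log relative risk. The impact is minor: no enrolment target, test or decision rule in the protocol uses the figure.

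**What to change.** Check the 10% entry with the method and inputs used for the other three rows of Table 8.2, then give the same value in the table and in the sentence after Table 8.3. If the table stands, replace 1.62 with 1.70 in the sentence. The case-control value of 1.91 already agrees with Table 8.3, so this point calls for no change there.

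The cost is one check and one corrected number. Design, data collection and the stated event count are unaffected. Figure 8.2 is not visible in the text reviewed, so no change to it is proposed; whoever makes the correction can see which value its 10% curve carries.
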